	1.6.3 Potential benefits	
2	STUDY OBJECTIVES	
3	STUDY DESIGN	9
	3.1 GENERAL DESIGN	9 9
4	SUBJECT SELECTION AND WITHDRAWAL	.10
	4.1 INCLUSION CRITERIA	.10 .11 .12 . 12
5	STUDY DRUG	.12
	5.1 DESCRIPTION 5.2 TREATMENT REGIMEN 5.3 METHOD FOR ASSIGNING SUBJECTS TO TREATMENT GROUPS 5.4 PREPARATION AND ADMINISTRATION OF STUDY DRUG 5.5 SUBJECT COMPLIANCE MONITORING 5.6 PRIOR AND CONCOMITANT THERAPY 5.7 PACKAGING 5.8 BLINDING OF STUDY DRUG 5.9 RECEIVING, STORAGE, DISPENSING AND RETURN 5.9.1 Receipt of Drug Supplies 5.9.2 Storage 5.9.3 Dispensing of Study Drug 5.9.4 Return or Destruction of Study Drug	.12 .12 .13 .13 .13 .13 .13
6	STUDY PROCEDURES	
•	6.1 VISIT 1	6 6
7	STATISTICAL PLAN	.14
	7.1 Sample Size Determination	.18

PHA Vers	RBIDOPA IN FAMILIAL DYSAUTONOMIA ASE II STUDY sion: 5.0 (date February 12, 2018) 7.2 STATISTICAL METHODS	
	SAFETY AND ADVERSE EVENTS	
8 8 8	3.1 DEFINITIONS	
9	8.6.1 Data Monitoring Committee DATA HANDLING AND RECORD KEEPING	
9 9 9	9.1 CONFIDENTIALITY 9.2 CONFIDENTIALITY AND HIPAA 9.3 SOURCE DOCUMENTS 9.4 CASE REPORT FORMS 9.5 RECORDS RETENTION	25 25 26
10	STUDY MONITORING, AUDITING, AND INSPECTING	26
•	10.1 STUDY MONITORING PLAN	
11	ETHICAL CONSIDERATIONS	26
12	STUDY FINANCES	27
1	12.1 FUNDING SOURCE	27
13	PUBLICATION PLAN	27
14	REFERENCES	27

Study Summary

Title	CARBIDOPA IN FAMILIAL DYSAUTONOMIA PHASE II STUDY, IND 117435, Date: 01/07/13
Short Title	CARBIFD
Protocol Number	13-00065
Phase	Phase 2
Methodology	Double-blind, Randomized, placebo control; cross-over design
Study Duration	3 years
Study Center(s)	Single-center
Objectives	The overall study objectives are to determine whether carbidopa (Lodosyn®) is safe and well tolerated and to assess whether it can inhibit catecholamine-induced paroxysmal hypertension and normalize or reduce the exaggerated blood pressure variability in patients with familial dysautonomia
Number of Subjects	30
Diagnosis and Main Inclusion Criteria	Diagnosis: Familial Dysautonomia ■ Male or female patients with FD age 10 or older ■ Unstable blood pressure: ■ Systolic BP standard deviation >15 mmHg ■ Or coefficient of variation >15% ■ Or documented episodic hypertensive peaks (≥140mmHg) ■ Confirmed diagnosis of FD (historical confirmation of subjects' genetic diagnosis will be obtained for this study) ■ Providing written informed consent (or ascent) to participate in the trial Ability to comply with the requirements of the study procedures.
Study Product, Dose, Route, Regimen	Carbidopa (Lodosyn®), Dose: 100mg, 200mg, placebo, oral, three time a day
Duration of administration	1 month on each dose.
Reference therapy	Placebo
Statistical Methodology	We will examine the sample distribution of SD of daytime SBP, and if it deviates from the normal distribution, we will employ the nonparametric Wilcoxon test for robustness. In addition, to account for potential covariates, such as age, gender, and disease severity, the analysis of (co)variance (ANOVA and ANCOVA) methods will be used to model the repeated measures data.

1 Introduction

Patients with the rare genetic disorder familial dysautonomia (FD) suffer from frequent surges in blood pressure that irreversibly damage their organs, for which there are no adequate treatments. This clinical trial will test whether carbidopa could effectively and safely treat the problematic high blood pressure. If successful, this will have a major impact in the quality of life of these patients, and could potentially be a treatment for other disorders of uncontrolled sympathetic activation.

This document is a protocol for a human research study. This study is to be conducted in accordance with US government research regulations, and applicable international standards of Good Clinical Practice, and institutional research policies and procedures.

1.1 Background

The study objective is to determine whether carbidopa (Lodosyn®) is safe and tolerable in patients with familial dysautonomia (FD), and to learn whether it can inhibit catecholamine-induced paroxysmal hypertension and reduce their exaggerated blood pressure (BP) variability. FD is a brutal genetic disease caused by a developmental defect in primary sensory neurons. The nerves that relay information from arterial baroreceptors are particularly affected resulting in unstable BP. Even mild anxiety can trigger a pronounced release of catecholamines causing paroxysmal hypertension and tachycardia. The subsequent exaggerated BP variability correlates closely with target organ damage in FD. Current drug treatments have little efficacy or intolerable side effects, and none specifically targets BP variability. Carbidopa is a reversible competitive inhibitor of aromatic L-amino acid decarboxylase (DOPA-decarboxylase). It cannot cross the blood brain barrier, and only prevents the formation of catecholamines in the periphery. We recently showed that carbidopa reduces the spillover of dopamine into the circulation and decreases the frequency of nausea in FD patients. Preliminary observations suggest that carbidopa may also lessen the exaggerated BP variability by reducing the formation of norepinephrine outside the brain. To follow up on this finding, we propose to conduct a well-powered study to test of the hypothesis that carbidopa might dampen norepinephrine-driven periods of paroxysmal hypertension in FD patients and thus lessen BP variability. We will use a randomized, double blind, 14-week cross over study comparing two doses of carbidopa and placebo. The sample size will be 30 patients with FD, who will act as their own controls across the two active doses and placebo. In random order, patients will receive high dose carbidopa (600 mg/day), low dose carbidopa (300 mg/day) or matching placebo in three separate 4-week treatment periods. We will monitor adverse events and safety/tolerability parameters throughout. The primary efficacy end-point will be the standard deviation of systolic BP variability. To understand the physiological effects of carbidopa we will measure 24-h catecholamine excretion and diurnal and short-term BP variability. If successful, this would be a major therapeutic breakthrough for FD patients, and could serve as the basis for the use of carbidopa in other more common BP disorders with similar pathophysiology.

The overall study objectives are to determine whether carbidopa (Lodosyn®) is safe and well tolerated and to assess whether it can inhibit catecholamine-induced paroxysmal hypertension and normalize or reduce the exaggerated blood pressure variability in patients with familial dysautonomia (FD, also called hereditary sensory and autonomic neuropathy type III or Riley-Day syndrome).¹

FD is a rare hereditary disorder caused by splice mutations that lead to a deficiency of elongator-1 protein (ELP-1 or IKAP).^{2,3} The defect prevents normal development of sensory (afferent) neurons,⁴ including those that relay information from arterial baroreceptors.⁵ Although reduced in number,⁶ when activated, the remaining efferent sympathetic nerves can dramatically raise blood pressure.^{1,5} Even mild arousals trigger surges in circulating catecholamines levels and characteristic paroxysmal hypertensive episodes.^{1,5,7} Patients also have orthostatic hypotension.

Renal failure is a major problem for patients with FD.⁸ Paroxysmal hypertension and excessive blood pressure fluctuations contribute to the progression of renal damage.^{9,10} Treatment of hypertension in patients with FD is fraught with difficulties. Clonidine and benzodiazepines are currently used to decrease emotionally-induced hypertension ¹¹ but they produce sedation, respiratory depression and dramatically worsen orthostatic hypotension.

We've recently shown that carbidopa, a reversible competitive inhibitor of DOPA-decarboxylase that does not cross the blood brain barrier, 12 successfully blocks the peripheral formation of dopamine and effectively reduced the frequency and severity of the retching/vomiting attacks, a disabling recurrent feature of these patients. 13 In

the small study, carbidopa was well tolerated and safe. New preliminary data indicates that carbidopa also reduces the synthesis of norepinephrine outside the brain in patients with FD. Further exploratory findings suggested that carbidopa might lessen the hypertensive peaks and reduce the exaggerate blood pressure variability over 24-hours, but further evidence is needed.

We now propose to perform a double-blind randomized trial with a cross over design to compare high dose (600 mg/day) and low dose (300 mg per day) carbidopa blockade with placebo. Patients will be randomly assigned to a high-dose/low-dose/placebo sequence, low-dose/placebo/high-dose sequence or placebo/high-dose/low-dose sequence. Participants will remain on each treatment period for 28-days.

Aim 1: To evaluate the safety and tolerability of carbidopa in FD patients with particular emphasis on the orthostatic fall in blood pressure.

Aim 2: As proof of concept, examine the hemodynamic effects of carbidopa and determine its effects on norepinephrine production, BP variability and paroxysmal hypertension.

Aim 3: In a dose finding study, compare the effects of low (300 mg/day) and high (600 mg/day) dose carbidopa blockade vs. placebo on BP variability and paroxysmal hypertension.

The study is well powered to answer whether carbidopa can successfully dampen norepinephrine-driven periods of paroxysmal hypertension, and compare the effectiveness of high-dose and low-dose blockade. As far as we are aware, this is the first time carbidopa has been used clinically to suppress norepinephrine synthesis in peripheral sympathetic neurons. If successful, effectively reducing catecholamine-driven paroxysmal hypertension without central side effects would be a major therapeutic breakthrough for these patients.

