1) Effect of Carbidopa on Blood Pressure Variability in FD:

Six of the 12 patients with FD that participated in the carbidopa nausea trial wore 24-hour ambulatory BP monitors while taking carbidopa (dose 450 to 600 mg/day, divided into three doses 6 hours apart). These patients were similar in age, gender and clinical features to the total population (mean age 18±2 years [range 15-28 years] 3 males: 3 females). In these 6-patients, we compared pre-treatment blood pressure recordings with those obtained while taking carbidopa. Overall average systolic (111±10 vs. 117±6 mmHg) and diastolic (73±3 vs. 70±8 mmHg) pressures were similar on and off carbidopa treatment, but heart rate was 13 beats lower while on carbidopa (86±3 to 76±2 bpm). While taking carbidopa, measures of blood pressure variability during the day were significantly lower (SD. p<0.05; coefficient of variation [CV] p<0.05, Fig. 4). Minimum captured BP was similar on and off carbidopa, but maximum captured BP was significantly lower on carbidopa (Fig. 4).

Page 6

Version: 5.0 (date February 12, 2018)

2) Effect of Carbidopa on Catecholamines in FD:

[figure not shown]

Fig. 5: Twenty-four hour noreprinephrine (NE) excretion before and after treatment with high-dose carbidopa

Twenty-four hour urinary catecholamine levels were assayed pre-treatment and after patients were titrated to their maximum tolerated dose. In addition to the expected decrease in dopamine excretion, norepinephrine excretion was also dramatically

[figure not shown]

Fig. 4: Graph A shows systolic blood pressure (SBP) variability (standard deviation SD) and graph B shows maximum SBP captured on an ambulatory recording before and after treatment with high-dose carbidopa.

excretion was also dramatically reduced (Fig. 5).

These results suggest that in patients with FD, inhibiting catecholamine synthesis upstream blunts the surges in norepinephrine as a knock on effect. We hypothesize, therefore, that by dampening the hypertensive peaks, carbidopa will reduces overall blood pressure variability in patients with FD.

We will carefully examine the hemodynamic effect of carbidopa and its effects on orthostatic hypotension. We will also determine whether a lower dose of carbidopa has similar beneficial effect.

Overview:

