1.5 Dose Rationale

Within 30 minutes of ingestion, carbidopa accumulates in the spleen, liver, lungs, kidneys and in plasma. ¹² Only half of the oral dose is absorbed ¹² and half-life in plasma is 1.3 hours. ³⁴ DOPA-decarboxylase activity remains inhibited up to 6 hours after dosage. ¹² In patients with FD, we are aiming for steady state of DOPA-decarboxylase

inhibition during waking hours when BP instability is at its most pronounced. In our previous trial, ¹³ we achieved this with a dosing schedule q6h (i.e., 7AM, 1PM and 7PM). In patients that were predictably hypertensive and at a certain time (most commonly when awakening from sleep when catecholamine levels surge), administration was tailored to 1.5 hours before awakening (via gastrostomy). In animal models, the mean effective dose of carbidopa needed to prevent L-DOPA-induced vomiting is 16 mg/kg (range 10 – 28 mg/kg). ⁴⁰ In adult patients with chronic autonomic failure, a dose of 200mg of carbidopa completely blocked the conversion of dihidroxyphenylserine (DOPS or droxidopa) to norepinephrine. ^{37,41} The same 200mg dose q6h (total daily dose: 600 mg) was effective at reducing norepinephrine excretion and BP variability in patients with FD (see preliminary data and ref: 13). We do not know if lower doses are as effective.

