7.2 Statistical Methods

We have a dedicated statistician for this clinical trial ([name], PhD). Our inclusion criteria use a baseline SD of systolic blood pressure variability ≥15 mmHg (2 SD above our age-matched control data [8.7±3 mmHg]). The mean coefficient of variation in 24-h BP readings in patients with FD is 19.1±5 and 99% of FD patients meet the inclusion criteria. Preliminary data shows that treatment with high dose carbidopa (600 mg/day) reduces blood pressure variability (SD of daytime SBP) by 7.0±5.5 mmHg. Power analysis for the primary outcome (reduction in SD of daytime SBP variability) is detailed in table 3. A sample size of 20 achieves 80% power to detect a reduction of 2.5 (or 2.9) from the null hypothesis of no reduction with an estimated standard deviation of 4.4 for the difference in SD at a significance level of 0.05 using a one-sided (or two-sided) one-sample t-test. The minimum detectable differences are all well below the observed reduction of BP fluctuation of 5.1 from our preliminary data. To ensure that the study is well powered, we will choose a sample size of 30 patients. To account for a drop out rate of around 15%, we will enroll 36 patients in the trial. We will examine the sample distribution of SD of daytime SBP, and if it deviates from the normal distribution, we will employ the nonparametric Wilcoxon test for robustness. In addition, to account for potential covariates, such as age, gender, and disease severity, the analysis of (co)variance (ANOVA and ANCOVA) methods will be used to model the repeated measures data.

Table 3: Power Calculation and Sample Size

Minimal detectable difference: SD BP variability high vs. low dose							
Sample size	T-test	T-test					
	One-sided	Two-sided					
20	-2.5	-2.9					
30	-2.0	-2.3					
40	-1.8	-2.0					

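### Section 1.1 calls the trial well powered to compare high-dose with low-dose carbidopa, but the benchmark behind that claim is a drug-versus-no-drug change, so the claim is unsupported

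*Combined protocol and SAP*

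**What the plan says.** After listing the aims, section 1.1 (Background) says: "The study is well powered to answer whether carbidopa can successfully dampen norepinephrine-driven periods of paroxysmal hypertension, and compare the effectiveness of high-dose and low-dose" carbidopa. Aim 3 is the dose-finding aim. Section 1.5 says that comparing the two doses will give preliminary data on which doses to take into a phase III trial.

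The power calculation is in section 7.2. It works "with an estimated standard deviation of 4.4 for the difference in SD", and the test is run "at a significance level of 0.05 using a one-sided (or two-sided) one-sample t-test". Table 3 carries the heading "Minimal detectable difference: SD BP variability high vs. low dose" and gives, for 30 patients, 2.0 mmHg (one-sided) and 2.3 mmHg (two-sided). The text then concludes: "The minimum detectable differences are all well below the observed reduction of BP fluctuation of 5.1 from our preliminary data". The same paragraph gives a second preliminary figure, a reduction of 7.0±5.5 mmHg in the SD of daytime systolic pressure at 600 mg/day.

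Section 1.4 describes the preliminary blood pressure data: six patients taking 450 to 600 mg/day. "In these 6-patients, we compared pre-treatment blood pressure recordings with those obtained while taking carbidopa". On the low dose, section 1.5 says: "We do not know if lower doses are as effective". Section 8.6.1 provides for an interim decision in case 300 mg/day proves as effective as 600 mg/day.

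**The concern.** Table 3 is labelled for the contrast between the two active doses, but the figure used to show that its detectable differences are comfortably small comes from a different contrast. A pre-treatment versus on-drug change is the whole effect of carbidopa plus anything else that changed between the recordings. The gap between 600 and 300 mg/day is only the part of that effect that the low dose fails to reach. It could be most of 5.1 mmHg or close to zero, and the plan gives no value for it. The margin between 2.3 and 5.1 therefore does not bear on power for the dose comparison.

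At stake is how the Aim 3 result is read. A reader who has been told that the comparison is well powered may take a non-significant difference as a sign that the lower dose does as well, and may carry that into the choice of doses for phase III.

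**Working it through.** **Inputs.** From section 7.2: SD of the within-patient difference 4.4 (no source given); alpha 0.05, with sidedness left open; 30 patients; benchmarks 5.1 and 7.0±5.5. I read 5.5 as a standard deviation, because the control figure in the same section (8.7±3, with the cut-off set 2 SD above it) works that way: 8.7 + 2 × 3 = 14.7, about 15. Two assumptions are mine: the fraction of the effect kept by the low dose, which no document gives, and that the stated SDs also hold for the difference between two active doses.

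**Step 1: reproduce Table 3.** The method is a one-sample t-test on paired differences, with power from the noncentral t distribution on n − 1 degrees of freedom and noncentrality δ√n / SD. Solving for δ at 80% power with SD 4.4:

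| n | One-sided, recomputed (printed) | Two-sided, recomputed (printed) |
|---|---|---|
| 20 | 2.54 (2.5) | 2.91 (2.9) |
| 30 | 2.05 (2.0) | 2.33 (2.3) |
| 40 | 1.76 (1.8) | 2.00 (2.0) |

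The table stands. Power at the printed values is 78.4% to 81.5%.

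**Step 2: high dose versus no drug.** With 30 patients, two-sided 0.05, power is above 99% for 5.1 or 7.0 with SD 4.4 or 5.5. This is the contrast to which the benchmarks belong.

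**Step 3: high versus low dose.** If the total effect is E and the low dose keeps a fraction f, the dose difference is δ = E × (1 − f). Example: E = 5.1 and f = 2/3 give δ = 1.70. With SD 4.4 the noncentrality is 1.70 × √30 / 4.4 = 2.12, against a critical value of 2.045, and power is 53%. The same calculation across the scenarios (n = 30, two-sided 0.05):

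| Low dose keeps | 5.1, SD 4.4 | 7.0, SD 5.5 | 7.0, SD 4.4 |
|---|---|---|---|
| 50% | 87% | 92% | 99% |
| two thirds | 53% | 61% | 80% |
| 75% | 34% | 39% | 56% |
| 80% | 23% | 27% | 39% |
| 90% | 9% | 10% | 13% |
| 100% | 5% | 5% | 5% |

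A one-sided test with 5.1 and SD 4.4 gives 66% at two thirds and 34% at 80%. Combining the smaller effect with the larger SD (5.1, SD 5.5), which section 7.2 does not do, gives 69% at half and 37% at two thirds.

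**Step 4: how much the low dose may keep at 80% power.** The largest fraction is 1 − (detectable difference / E). For 5.1 and SD 4.4: 1 − 2.33/5.1 = 54%. For 7.0 and SD 5.5, where the detectable difference is 2.91: 1 − 2.91/7.0 = 58%. For 7.0 and SD 4.4: 1 − 2.33/7.0 = 67%.

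**Step 5: precision.** The expected half-width of a 95% confidence interval for the dose difference is 2.045 × 4.4 / √30 = 1.64 mmHg.

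**The case against.** The plan does disclose the key number. Table 3 is headed for the dose contrast and prints 2.3 mmHg, so a careful reader can see what difference the trial can detect. Any superiority comparison loses power as the true difference shrinks, and the retention fractions above are scenarios, not data. If the low dose keeps half the effect or less, the comparison has good power. Section 1.5 also calls the dose information preliminary. All of this stands. It does not supply what the sentence in section 1.1 needs, which is a reason to expect a dose difference of 2.3 mmHg or more.

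Several stronger readings are tempting, and the documents do not support them:

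- **That the dose comparison is underpowered.** The low-dose effect is unknown, so adequate power cannot be ruled out any more than it can be claimed.
- **That power is 23% to 53% once the low dose keeps two thirds or more.** That range covers only two thirds to 80% kept, on one of the input pairs. On that pair power is at most about 53% and falls towards 5% as the doses converge. With 7.0 and SD 4.4 it is 80% at two thirds.
- **That a non-significant result is likely when a third of the benefit is lost.** On the three pairs, significance at that point has a probability of 53% to 80%.
- **That the plan commits to reading non-significance as equality.** No section says so. The interim provision in section 8.6.1 does not define equal effectiveness, and it leads only to a decision taken with the monitoring board.
- **That the calculation is wrong.** Table 3 reproduces.

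One link is inferred. The readable text of section 1.4 does not print 5.1 (its figure is not reproduced), so the source of 5.1 is not shown. But the documents describe no preliminary blood pressure data on 300 mg/day, so 5.1 cannot be a high-low difference.

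**Conclusion.** Wrong as written: an unsupported power statement, not an arithmetic error. The detectable differences are correct but are set against a drug-versus-no-drug change, and the plan states no expected or smallest relevant difference between the doses. It also treats similar dose effects as possible (sections 1.5 and 8.6.1).

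The size depends on the unknown low-dose effect. Power for the dose comparison reaches 80% only if the low dose keeps no more than about 54% to 67% of the effect, depending on the input pair. At 75% kept it is 34% to 56%, and at half or less it is at least 87%. These figures assume 30 evaluable patients, a two-sided 0.05 paired t-test, and that the stated SDs apply between doses.

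**What to change.** In section 1.1, limit the well-powered statement to 600 mg/day versus placebo. It should not be widened to active drug versus placebo: there are no blood pressure data on 300 mg/day, and if that dose kept only a third of a 5.1 mmHg effect, low dose versus placebo would have the same 53% power (5.1 × 1/3 = 1.70 mmHg).

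In section 7.2:

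- Say that 5.1 and 7.0 are uncontrolled pre-treatment versus on-drug changes, and that they do not apply to the high-low or low-placebo contrasts.
- State the dose comparison on its own terms, for example: *With 30 patients the high-low comparison has 80% power (two-sided 0.05) only for a difference of at least 2.3 mmHg if the SD is 4.4, or about 2.9 mmHg if it is 5.5. On the first SD this means that the low dose achieves about half or less of a 5.1 mmHg effect.*
- Report the high-low difference with its 95% confidence interval (expected half-width about 1.6 mmHg at SD 4.4), and state that a non-significant difference will not be read as equal effectiveness.

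Relabelling Table 3 alone would leave the sentence in section 1.1 without support. The change needs wording in two sections and one interval in the report, with no extra patients or procedures. The only cost is a less favourable power statement for the dose comparison.
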